 - a. Absolute neutrophil count (ANC) \geq 1,500/mm³; Patients must be able to meet the criteria without receipt of colony stimulating factors within 2 weeks before obtaining sample
 - b. Platelets \geq 100,000/mm³; Patients must be able to meet the criteria without receipt of transfusion within 2 weeks before obtaining sample
 - c. Hemoglobin \geq 9 g/dL; Patients must be able to meet the criteria without receipt of transfusion within 2 weeks before obtaining sample
16. Serum creatinine clearance \geq 55 mL/min based on Cockcroft-Gault equation
17. Adequate hepatic parameters:
 - a. Aspartate aminotransferase (AST) and/or Alanine aminotransferase (ALT) \leq 3 x ULN
 - b. Total serum bilirubin \leq 1.5 x ULN, except for patients with a documented history of Gilbert's Syndrome who can be enrolled at PI discretion
 - c. For patients with liver metastases, AST and ALT \leq 5x the institution's ULN and/or total bilirubin \leq 3.0x the institution's ULN are acceptable as long as there is no persistent nausea, vomiting, right upper quadrant pain or tenderness, fever, or rash.
18. Alkaline phosphatase \leq 2.5 x ULN (\leq 5.0 x ULN if bone metastases present)
19. Resolution of all acute toxic effects of prior therapy, including radiotherapy to grade \leq 1 or patient's baseline (except toxicities not considered a safety risk for the patient) and recovery from surgical procedures.
20. Must have discontinued all previous therapies for cancer (including endocrine therapy, CDK4/6 inhibitor therapy, cytotoxic chemotherapy, targeted therapy [including, but not limited to, everolimus], radiotherapy, immunotherapy, and investigational therapy) for at least 14 days prior to receiving study drugs.

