3.3. Exclusion Criteria

1. Concurrent therapy with other approved or investigational cancer treatment agents, except bisphosphonates, RANKL inhibitors, GnRH agonists such as leuprolide or goserelin.
2. Inability to comply with study requirements.

3. Diagnosis of other invasive cancer except for adequately treated cervix cancer, or more than 5 years since other diagnosis of invasive cancer (including invasive squamous cell cancers due to contraindication for methoxsalen use) without current evidence of disease.
4. Pregnant women or women of childbearing potential without a negative pregnancy test (serum or urine) within 14 days prior to starting study treatment.
5. Breastfeeding must be discontinued prior to study entry.
6. Impairment of gastrointestinal (GI) function or GI disease that may significantly alter the absorption of the study drugs (e.g., ulcerative diseases, uncontrolled nausea/vomiting, chronic diarrhea, malabsorption syndrome, intestinal obstruction, or small bowel resection) at discretion of investigator.
7. Patients with clinically significant liver disease, including active viral (including hepatitis B, hepatitis C, etc) or other known active hepatitis, current alcohol abuse, or cirrhosis.
8. Known chronic hepatitis B virus infection (testing not required prior to enrollment).
 - a. Patients with chronic hepatitis C virus infection may be enrolled if there is no clinical/laboratory evidence of cirrhosis per investigator AND the patient's liver function tests fall within the parameters set in the inclusion criteria, Section 3.2.
9. Uncontrolled HIV infection defined as any of the following 3 criteria: CD4 counts \leq 350 cells/ μ L; serum HIV viral load \geq 400 copies/mL; on a antiretroviral regimen for $<$ 4 weeks prior to treatment with study drugs if anti-retroviral therapy is deemed necessary or appropriate by the investigator.
10. Previous enrollment in this study or any other study investigating SM-88.
11. History of any known drug allergies to any study medication.
12. Clinically significant and uncontrolled major medical condition(s) including, but not limited to uncontrolled nausea/vomiting/diarrhea; active, uncontrolled infection; symptomatic congestive heart failure (New York Heart Association [NYHA] class \geq II); unstable angina pectoris; cardiac arrhythmia requiring hospitalization in the past 3 months; stroke or MI in the past 6 months.

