Grade 1 and 2	No requirement for dose interruption or dose reduction
Anemia Grade \geq 3 (hemoglobin < 8 g/dL or transfusion indicated)	
1st occurrence: Hold SM-88 and MPS; monitor at least weekly and if hemoglobin recovers to ≥ 8 g/dL within 28 days then resume drugs and decrease SM-88 to dose level -1. Transfusion of blood and blood products are permitted.Recurrence: Hold SM-88 and MPS; monitor at least weekly and if hemoglobin recovers to ≥ 8 g/dL within 28 days resume drugs and patient can remain on study at investigator discretion.Permanently discontinue SM-88 and MPS if these parameters have not been met after 28 days of dose interruption.
Neutropenia Grade \geq 3 (ANC $< 1000/\text{mm}^3$) associated with a documented infection or fever $\geq 38.5^\circ\text{C}$	
1st occurrence: Hold SM-88 and MPS; monitor at least weekly and if ANC recovers ($\text{ANC} \geq 1000/\text{mm}^3$) within 28 days, then resume drugs and decrease SM-88 to dose level-1. Hematopoietic growth factors are not permitted.Recurrence: Hold SM-88 and MPS; monitor at least weekly and if ANC recovers ($\text{ANC} \geq 1000/\text{mm}^3$) within 28 days then resume drugs at same dose level.Permanently discontinue SM-88 and MPS if these parameters have not been met after 28 days of dose interruption.
Grade 4 neutropenia (ANC $< 500/\text{mm}^3$)	
1st occurrence: Hold SM-88 and MPS. Monitor at least weekly and if ANC recovers to $\geq 1000/\text{mm}^3$ in ≤ 7 days, then resume study drugs at same dose level. If ANC remains $< 1000/\text{mm}^3$ for > 7 days, hold SM-88 and MPS until ANC $\geq 1000/\text{mm}^3$ and decrease SM-88 to dose level -1.Recurrence: Hold SM-88 and MPS; monitor at least weekly and if ANC recovers ($\text{ANC} \geq 1000/\text{mm}^3$) within 28 days then decrease SM-88 to dose level -1 or resume drugs at same dose level if already at dose level -1.Permanently discontinue SM-88 and MPS if these parameters have not been met after 28 days of dose interruption.

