Thrombocytopenia Grade \geq 3 (platelets $< 50,000/\text{mL}$)	
Hold SM-88 and MPS; monitor at least weekly and if platelets recover ($\geq 50,000/\text{mL}$) within 28 days, then resume drugs at same dose level.If Grade 3 thrombocytopenia (platelets $< 50,000/\text{mL}$) with bleeding, hold SM-88 and MPS. Monitor at least weekly and if platelets recover ($\geq 50,000/\text{mL}$) and bleeding stops within 28 days, resume drugs and decrease SM-88 to dose level -1.If Grade 4 thrombocytopenia (platelets $< 25,000/\text{mL}$), hold SM-88 and MPS. Monitor at least weekly and if platelets recover ($\geq 50,000/\text{mL}$) within 28 days, resume drugs and decrease SM-88 to dose level -1.Permanently discontinue SM-88 and MPS if Grade ≥ 3 thrombocytopenia (platelets $< 50,000/\text{mL}$) recurs or persists for > 28 days.
Non-hematologic Toxicities	
Grade 1 and 2	
No requirement for dose interruption or dose reduction.
Grade ≥ 3	
1st occurrence: Hold SM-88 and MPS; monitor and if toxicity decreases to Grade 1 or to baseline within 28 days, then resume drugs and decrease by SM-88 to dose level -1.

	
 • Recurrence: Hold SM-88 and MPS; monitor and if toxicity decreases to Grade 1 or to baseline within 28 days then resume drugs at same dose level. • Exceptions are: Nausea, vomiting, or diarrhea lasting ≤72 hours; fatigue lasting ≤ 7 days; hypertension controlled with medical therapy; increase in indirect bilirubin indicative of Gilbert's syndrome; serum lipase or amylase lasting ≤ 7 days without clinical signs or symptoms of pancreatitis; endocrinopathies controlled with hormonal therapy; laboratory values that do not have any clinical correlate.
--	---

All dose modifications should be clearly documented in the patient's medical chart and in the CRF.

6. Safety Variables and toxicity assessment

The Principal Investigator or Sub-Investigators will assess adverse events, laboratory data, and vital signs throughout the study. Adverse events will be assessed by NCI CTCAE Version 5.0.

https://ctep.cancer.gov/protocoldevelopment/electronic_applications/docs/CTCAE_v5_Quick_Reference_5x7.pdf

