6.8. General Management of Significant Toxicities

6.8.1. Significant Toxicities Management

The following are general guidelines for dose delay and discontinuation of the study drugs if a patient experiences an adverse event; Refer to **Table 5** for specific guidance:

- Patients may delay treatment for up to 28 days to allow the toxicity to resolve. If the toxicity requiring dose interruption has not resolved completely or to CTCAE Grade 1 (or to baseline if Grade 2 at time of study entry) during the maximum 28-day dose interruption period, the patient must permanently discontinue treatment on study
- Patients may restart therapy if toxicity(ies) resolve to Grade 1 or lower (or to baseline if Grade 2 at time of study entry).
- If a dose interruption is required at any point on study because of hematologic toxicity, weekly blood draws for CBC will be monitored until the AE resolves or the patient comes off study.
- The patient must be referred to a hematologist for further evaluation (1) if frequent (at investigator discretion) transfusions are required or (2) if the treatment-related hematologic toxicities have not recovered to CTCAE Grade 1 or less after 28 days.
- For major surgery while on treatment, up to 28 days of study treatment interruption is allowed.
- All dose interruptions (including any missed doses), and the reasons for the reductions/interruptions, are to be recorded.

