 	
Willingness to utilize adequate contraception if of childbearing potential. Women of childbearing potential must use adequate contraception for the duration of protocol treatment and for at least 6 months after the last treatment with SM-88 used with MPS. Men must not donate sperm or conceive a child for the duration of protocol treatment and for at least 6 months after the last treatment with SM-88 used with MPS.
 
 ○ Adequate contraception is defined as one highly effective form (i.e. abstinence, (fe)male sterilization) OR two effective forms (IUD [non-hormonal preferred], condom with spermicidal foam / gel / film / cream / suppository, occlusive cap with spermicidal foam / gel / film / cream / suppository).
 	Must be able and willing to swallow pills whole and retain oral medication.
 	Resolution of all acute toxic effects of prior therapy, including radiotherapy to grade \leq 1 or patient's baseline (except toxicities not considered a safety risk for the patient) and recovery from surgical procedures.
 	Must have discontinued all previous therapies for cancer (including endocrine therapy, CDK4/6 inhibitor therapy, cytotoxic chemotherapy, targeted therapy [including, but not limited to, everolimus], radiotherapy, immunotherapy, and investigational therapy) for at least 14 days prior to receiving study drugs.

LAB VALUES (ALL MUST BE CHECKED YES)

YES NO	
 	ANC \geq 1,500/mm 3 ; Patients must be able to meet the criteria without receipt of colony stimulating factors within 2 weeks before obtaining sample
 	Platelets \geq 100,000/mm 3 ; Patients must be able to meet the criteria without transfusion within 2 weeks before obtaining sample
 	Hemoglobin \geq 9.0 g/dL; Patients must be able to meet the criteria without transfusion within 2 weeks before obtaining sample
 	Creatinine clearance \geq 55 mL/min based on Cockcroft-Gault equation

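### Table 5 gives all seven platelet limits per mL where per mm³ is evidently meant: a minor unit correction to an operative dosing threshold

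*Combined protocol and SAP*

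**What the plan says.** Section 5.6 sends the reader to Tables 4 and 5 for changes to SM-88 dosing after a grade 3 or 4 toxicity. The thrombocytopenia row of Table 5 has a label and four bullets. The first bullet says to hold all drugs, monitor at least weekly, and "if platelets recover ($\geq 50,000/\text{mL}$) within 28 days, then resume drugs at same dose level". The third reads "If Grade 4 thrombocytopenia (platelets $< 25,000/\text{mL}$), hold SM-88 and MPS". The second covers Grade 3 with bleeding and the fourth covers permanent discontinuation. Every platelet count in the row is per mL.

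Other blood-count limits use a different unit. The neutropenia row just above reads "Neutropenia Grade \geq 3 (ANC $< 1000/\text{mm}^3$) associated with a documented infection or fever", and the Grade 4 neutropenia row is also per mm³. The platelet entry criterion, Section 3.2 item 15b, is at least "100,000/mm³; Patients must be able to meet the criteria without receipt of transfusion", and the Appendix A checklist gives the same platelet limit per mm³. Nothing in the document corrects or explains the per-mL unit.

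**The concern.** A hold limit and an entry limit for the same blood count should be on the same scale. Here they differ in unit by a factor of 1,000. The row governs interruption, restart, SM-88 reduction and permanent stop for all four study drugs, and Section 6.8.1 refers the reader to Table 5 for the specifics, so this is working text and not background. Thrombocytopenia is also a named risk: Section 6.8.3.1 lists it among the blood complications reported with phenytoin. If someone applied the numbers exactly as written, the numeric hold would almost never trigger.

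**Working it through.** **Inputs**

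- Platelet limits: Table 5, thrombocytopenia row.
- Platelet entry limit: 100,000/mm³ (Section 3.2 item 15b; Appendix A).
- Neutrophil limits: entry 1,500/mm³ (Section 3.2 item 15a); hold below 1,000/mm³ and Grade 4 below 500/mm³ (Table 5).
- Conversion: 1 mL = 1 cm³ = 1,000 mm³, so count per mm³ = count per mL ÷ 1,000.

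**Count and conversion of the limits**

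| Place in the row | Role | As given | Literal value per mm³ |
|---|---|---|---|
| Row label | hold | < 50,000/mL | < 50 |
| Bullet 1 | resume | ≥ 50,000/mL | ≥ 50 |
| Bullet 2, Grade 3 with bleeding | hold | < 50,000/mL | < 50 |
| Bullet 2 | resume | ≥ 50,000/mL | ≥ 50 |
| Bullet 3, Grade 4 | hold | < 25,000/mL | < 25 |
| Bullet 3 | resume | ≥ 50,000/mL | ≥ 50 |
| Bullet 4 | permanent stop | < 50,000/mL | < 50 |

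That is seven limits: six at 50,000 and one at 25,000; four hold or stop limits and three resume limits. The conversions are 50,000 ÷ 1,000 = 50 and 25,000 ÷ 1,000 = 25.

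**Comparison with the entry limit**

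- Literal per mL: 100,000 ÷ 50 = 2,000. A patient at the entry limit would have to lose (100,000 − 50) ÷ 100,000 = 99.95% of the count before the numeric hold applied.
- Per mm³: 100,000 ÷ 50,000 = 2. The fall needed is (100,000 − 50,000) ÷ 100,000 = 50%.
- Neutrophils, for scale: 1,500 ÷ 1,000 = 1.5.

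Only the per-mm³ reading puts the platelet rule on the same scale as the entry criterion and the neutrophil rule.

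**What else fixes the meaning**

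All four hold or stop limits are tied to a grade in the same phrase: Grade ≥ 3, Grade 3, Grade 4 and Grade ≥ 3. Section 6 names CTCAE version 5.0 for grading. Section 5.6 starts SM-88 dose changes at grade 3 or 4. Section 6.8.1 allows restart on recovery to Grade 1 or lower (or to baseline if Grade 2 at entry). If toxicity has not resolved that far "during the maximum 28-day dose interruption period, the patient must permanently discontinue treatment on study".

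**The case against.** The first objection is that the point turns on one letter. The available text was read from PDF by a program, and µL misread as mL would give exactly this picture, since one µL is one mm³. Seven agreeing readings are weak evidence, because all seven stand in one row in the same notation and could share one fault. This stands as a reason to look at the page before amending. The balance is nevertheless against a misreading. Section 3.3 item 9 gives the CD4 count per µL and, in the same item, "serum HIV viral load \geq 400 copies/mL"; the Appendix A checklist keeps the two apart as well. The micro sign also survives in the µg doses of Section 1.3, and mm³ survives in Table 5 itself.

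The second objection concerns consequence. A reader might infer that the row cannot be applied at all. The documents do not support that: each hold or stop limit comes with its grade, so a site can apply the row by CTCAE grade, and would very probably read the numbers per mm³ anyway.

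A reader might also infer that patients could be restarted at almost any platelet count. That needs a mixed reading, with the hold taken by grade and the resume limit taken literally per mL, although the resume limit is the exact complement of the row's own Grade ≥ 3 limit. The word recover in the bullet and the restart and stop rules of Section 6.8.1 make it less plausible still. Section 6.8.1 does not repair the unit, because it is general guidance that defers to Table 5, but it does limit the practical risk.

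**Conclusion.** The point holds as a minor unit correction. As the text reads, seven of seven platelet limits are 1,000-fold too low when taken literally: 50/mm³ and 25/mm³ in place of 50,000/mm³ and 25,000/mm³. That per mm³ was intended is an inference, but a strong one, from the entry limit, the neutrophil rows and the grade labels. The 1,000-fold figure and the 99.95% fall measure the size of the slip; they do not measure how far patients were under-protected, and the documents give no ground for saying that they were. The risk of actual harm is low. The two-stage response rule, its error rates and the efficacy analyses contain no platelet limit and are unaffected. The conclusion assumes that the source page reads mL; if it reads µL, there is nothing to correct.

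**What to change.** Check the source page of Table 5 first. If it reads mL, change /mL to /mm³ at all seven places in the thrombocytopenia row, so that the limits become < 50,000/mm³ (three places), ≥ 50,000/mm³ (three places) and < 25,000/mm³ (one place). Note the correction to sites in the next amendment. The cost is seven unit changes in one row and one line in the amendment summary, with no new procedure, data or patients.

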5.6. Recommended Dose Modifications

Every effort should be made to administer each investigational product at the planned dose and schedule.

In the event of significant toxicity, dosing may be interrupted, delayed and/or reduced, only as described for each investigational product. In the event of multiple toxicities, treatment/dose modifications should be based on the worst toxicity observed. Patients are to be instructed to notify Investigators at the first occurrence of any adverse symptom.

Treatment/dose modifications may occur independently for each investigational product in the combination based on the observed toxicity and the general guidance, as follows:

- a. SM-88: Dose modifications (dose interruptions, or dose reductions) may be implemented to manage toxicities.
 - i. If SM-88 is held then MPS should be held concurrently.
- b. Methoxsalen, phenytoin, and sirolimus (MPS): No dose reductions are permitted in this study, but if methoxsalen, phenytoin, or sirolimus are considered to be the component associated with a grade 3 or 4 toxicity, the individual components may be discontinued for up to 28 days while mitigating measures are attempted (e.g. changing the timing of phenytoin to address phenytoin related fatigue if experienced). This may be applied to any or all of the MPS components. If after 28 days the grade > 2 toxicity continues, the patient will be removed from the study. If the patient restarts the MPS medication(s) but the toxicity recurs then the 28 day hold clock restarts so that further mitigation efforts can be implemented; if multiple holds are required then it is at investigator discretion if the patient should continue or come off the study.
 - i. If any or all components of MPS are held then SM-88 can be continued at investigator discretion.

The RP2D of SM-88 is 920 mg/day administered as two 230 mg capsules every 12 hours. For patients experiencing a grade 3 or 4 toxicity, dose modifications of SM-88 can be made as outlined in **Table 4 and Table 5**.

Table 4. Dose Modifications for Toxicities Related to SM-88

Dose Level	SM-88 Dose	Dose Adjustment for Next Treatment
1	460 mg BID (920 mg/day)	Decrease dose to 230 mg BID
-1	230 mg BID (460 mg/day)	Discontinue study treatment for up to 28 days and attempt mitigation; if this dose is not tolerated then patient should be removed from the study

Table 5. Management of Toxicities Related to SM-88 and MPS

	SM-88 + MPS
Hematologic Toxicities	

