6.8.3. Detailed Descriptions of Potential Adverse Events associated with MPS

6.8.3.1. Related to Phenytoin

Withdrawal Precipitated Seizure, Status Epilepticus

Abrupt withdrawal of phenytoin in epileptic patients may precipitate status epilepticus. When, in the judgment of the clinician, the need for dosage reduction, discontinuation, or substitution of alternative anticonvulsant medication arises, this should be done gradually. However, in the event of an allergic or hypersensitivity reaction, more rapid substitution of alternative therapy may be necessary. In this case, alternative therapy should be an anticonvulsant not belonging to the hydantoin chemical class.

Suicidal Behavior and Ideation

Phenytoin can increase the risk of suicidal thoughts or behavior in patients. Patients should be monitored for the emergence or worsening of depression, suicidal thoughts or behavior, and/or any unusual changes in mood or behavior. The increased risk of suicidal thoughts or behavior can occur as early as one week after starting treatment and persist for the duration of treatment. Should suicidal thoughts and behavior emerge during treatment, Investigators need to consider whether the emergence of these symptoms in any given patient may be related to the disease being treated. Patients, their caregivers, and families should be informed that AEDs increase the risk of suicidal thoughts and behavior and should be advised of the need to be alert for the emergence of or worsening of the signs and symptoms of depression, any unusual changes in mood or behavior, the emergence of suicidal thoughts, behavior, or thoughts about self-harm. Behaviors of concern should be reported immediately to healthcare providers.

Serious Dermatologic Reactions

Serious and sometimes fatal dermatologic reactions, including TEN and SJS, have been reported with phenytoin treatment. The onset of symptoms is usually within 28 days but can occur later. Phenytoin should be discontinued at the first sign of a rash, unless the rash is clearly deemed not drug-related. If signs or symptoms suggest SJS/TEN, phenytoin should be discontinued and not re-administered. If a rash occurs, the patient should be evaluated for signs and symptoms of Drug Reaction with Eosinophilia and Systemic Symptoms (DRESS) (see next paragraph).

Drug Reaction with Eosinophilia and Systemic Symptoms (DRESS)/Multiorgan hypersensitivity

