DRESS, also known as Multiorgan hypersensitivity, has been reported in patients taking phenytoin. Some of these events have been fatal or life-threatening. DRESS typically, although not exclusively, presents with fever, rash, and/or lymphadenopathy, in association with other organ system involvement, such as hepatitis, nephritis, hematological abnormalities, myocarditis, or myositis sometimes resembling an acute viral infection. Eosinophilia is often present. Because this disorder varies in its expression, other organ systems not noted here may be involved, and it is important to note that early manifestations of hypersensitivity, such as fever or lymphadenopathy, may be present even though rash is not evident. If such signs or symptoms are present, the patient should be evaluated immediately. Phenytoin should be discontinued and not re-administered if an alternative etiology for the signs or symptoms cannot be established.

Hypersensitivity

Patients with a history of hypersensitivity to phenytoin, its inactive ingredients, or other hydantoins; or a history of prior acute hepatotoxicity attributable to phenytoin, are excluded from this trial (see Exclusion Criteria). If there is a history of hypersensitivity reactions to structurally similar drugs, such as carboxamides (e.g., carbamazepine), barbiturates, succinimides, and oxazolidinediones (e.g., trimethadione) in the patient or

immediate family members, care must be taken to avoid potential patients' hypersensitivity to phenytoin. Discontinue and do not re-administer phenytoin if patients exhibit hypersensitivity to phenytoin during the study.

Hepatic Injury

Cases of acute hepatotoxicity, including infrequent cases of acute hepatic failure, have been reported with phenytoin. These events may be part of the spectrum of DRESS or may occur in isolation. Other common manifestations include jaundice, hepatomegaly, elevated serum transaminase levels, leukocytosis, and eosinophilia. The clinical course of acute phenytoin hepatotoxicity ranges from prompt recovery to fatal outcomes. In these patients with acute hepatotoxicity, phenytoin should be immediately discontinued and not re-administered.

Hematopoietic Complications

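### Table 5 tells sites to resume MPS after any recovered Grade ≥3 non-hematologic toxicity, without excepting the reactions after which section 6.8.3 bars or ends phenytoin or sirolimus dosing

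*Combined protocol and SAP*

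**What the plan says.** Table 5 in section 5.6 is titled "Management of Toxicities Related to SM-88 and MPS". In its non-hematologic Grade ≥3 row, sites hold SM-88 and MPS. At first occurrence, "if toxicity decreases to Grade 1 or to baseline within 28 days, then resume drugs and decrease by SM-88 to dose level -1". At recurrence, "if toxicity decreases to Grade 1 or to baseline within 28 days then resume drugs at same dose level". The row then lists exceptions for short-lived, controlled or laboratory-only events.

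Section 6.8.3.1 gives different instructions for phenytoin after particular reactions:

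- Severe skin reactions: "If signs or symptoms suggest SJS/TEN, phenytoin should be discontinued and not re-administered".
- DRESS: "Phenytoin should be discontinued and not re-administered if an alternative etiology for the signs or symptoms cannot be established".
- Hypersensitivity: "Discontinue and do not re-administer phenytoin if patients exhibit hypersensitivity to phenytoin during the study".
- Liver injury: "In these patients with acute hepatotoxicity, phenytoin should be immediately discontinued and not re-administered".
- Acute toxicity with serum levels above the therapeutic range: because the single 50 mg tablet leaves no room to reduce the dose, phenytoin is ended.

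Section 6.8.3.3 forbids giving sirolimus again after hypersensitivity or fluid accumulation, and ends sirolimus dosing if angioedema occurs.

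Section 6.8.1 gives general rules for delay and restart and points to Table 5 for the specifics. Section 5.6(b) allows an MPS component to be held for up to 28 days. The note in 4.3.12 allows the other drugs to continue if one MPS agent has to be dropped.

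**The concern.** The drugs held under the Table 5 row include phenytoin and sirolimus, so an instruction to resume the drugs on recovery covers them too. For a patient whose reaction falls under one of the 6.8.3 rules, that is the opposite of what 6.8.3 requires.

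The stake is patient safety. The protocol says of the skin reactions: "Serious and sometimes fatal dermatologic reactions, including TEN and SJS, have been reported with phenytoin treatment". It also describes some DRESS events as fatal or life-threatening, and the course of acute phenytoin hepatotoxicity as reaching fatal outcomes. Sites are likely to use a management table as the working rule, particularly when 6.8.1 sends them to it.

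**Working it through.** No sample size, power or error rate is involved, and the plan states no figure to reproduce. The check is a comparison of texts.

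**Step 1. When the conflict arises.** Three conditions must hold together: the event is non-hematologic and Grade ≥3; it recovers to Grade 1 or baseline within 28 days; and it falls under a 6.8.3 stop rule for phenytoin or sirolimus. If the event has not recovered by 28 days, 6.8.1 makes permanent discontinuation mandatory, so the restart instruction is not reached.

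**Step 2. The stop rules in 6.8.3 against the Table 5 row.**

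| Drug | Reaction | 6.8.3 instruction | Named in the Table 5 exceptions? |
|---|---|---|---|
| Phenytoin | Suspected SJS/TEN | Do not give again | No |
| Phenytoin | DRESS signs, no other cause established | Do not give again | No |
| Phenytoin | Hypersensitivity | Do not give again | No |
| Phenytoin | Acute hepatotoxicity | Do not give again | No |
| Phenytoin | Acute toxicity, levels above range | End dosing | No |
| Sirolimus | Hypersensitivity | Do not give again | No |
| Sirolimus | Fluid accumulation | Do not give again | No |
| Sirolimus | Angioedema | End dosing | No |

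Explicit bars on re-administration: 4 (phenytoin) + 2 (sirolimus) = 6. Termination rules: 1 + 1 = 2. Total rules: 6 + 2 = 8.

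**Step 3. What the exceptions cover.** There are seven clauses: brief nausea, vomiting or diarrhea; brief fatigue; controlled hypertension; indirect bilirubin in Gilbert's syndrome; brief lipase or amylase rises; controlled endocrinopathies; and laboratory values without a clinical correlate. They name 0 of the 8 rules. They also work in the other direction, releasing events from the hold and reduction rather than stopping a component for good.

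**Step 4. Overlap.** The eight are rules, not eight separate reactions. Section 6.8.3.3 lists angioedema among the sirolimus hypersensitivity reactions. Section 6.8.3.1 gives multiorgan hypersensitivity as another name for DRESS, and says that liver events may belong to the DRESS spectrum.

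**Step 5. One rule is unlikely to apply.** Section 1.4.4 gives a highest observed phenytoin level of 1,420 ng/mL in Part 1 of the pancreatic cancer trial. The top of the therapeutic range is 20,000 ng/mL, and 1,420 / 20,000 = 7.1%. Assuming the same phenytoin dose there, above-range toxicity at 50 mg/day is improbable.

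**Step 6. Does other text resolve the conflict?**

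- 5.6(b) permits a hold of up to 28 days and foresees a restart, but names no reaction for which restart is barred.
- 6.8.1 permits restart on recovery and refers to Table 5, not to 6.8.3.
- 4.3.12 says what may happen once an MPS agent has to be dropped, not when it must be.
- 6.3.4.3 requires each event to be attributed to a drug, which can lead a site to 6.8.3 but does not settle which rule governs.

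No sentence gives 6.8.3 precedence over Table 5.

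**The case against.** The best defence is that the two places can be read together. Section 5.6 is headed as recommendations, and the sentence introducing Tables 4 and 5 is permissive and speaks of modifying SM-88. MPS has its own paragraph, 5.6(b). The 6.8.3 stops are directive and specific to drug and event, and a specific prohibition is usually taken to limit a general recovery rule. Attribution by drug and the 4.3.12 note make it workable to drop one component. To go wrong, an investigator would have to rechallenge against an explicit prohibition in the same protocol. Section 1.3 reports 77 patients given SM-88 with MPS and no specific risks, and the DSMC reviews the trial quarterly.

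Much of this stands, and it lowers the chance of harm. It does not remove the conflict. The table's title and the row itself name MPS, and 6.8.1 treats Table 5 as the place for specifics. Table 5 also states permanent stops elsewhere, for example for recurrent Grade ≥3 thrombocytopenia, so a reader could take their absence from this row as intended. Seventy-seven patients are too few to exclude rare reactions.

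The defence is also right that 6.8.1 is not merely permissive. Its 28-day stop is mandatory, so any exception that lets the other drugs continue must keep that condition.

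**Conclusion.** The Table 5 row is wrong as written, as a matter of patient safety only. Followed literally, it restarts phenytoin or sirolimus after reactions for which 6.8.3 says the drug must not be given again or must be ended. The gap is 0 of 8 overlapping rules excepted: six explicit bars and two termination rules. This is a should-fix at the next amendment.

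The conclusion assumes that the drugs to be resumed are the drugs the row has just put on hold, and that 6.8.3 is meant to bind sites.

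Stronger readings that the documents do not support:

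- *The protocol lacks these safety rules, so the matter is urgent.* The rules are in 6.8.3 in directive words. What is missing is the exception in the row and a statement of which text governs.
- *Eight distinct reactions are overlooked.* The rules overlap, and the above-range phenytoin rule is unlikely to be triggered.
- *5.6(b) and 6.8.1 contradict 6.8.3 as well.* Their restart wording permits rather than orders, so they need only a cross-reference.
- *The conflict extends to Grade 1 and 2 events or to any rash.* The restart rule applies to Grade ≥3, and the instruction to stop phenytoin at the first sign of a rash does not itself bar a restart.
- *A number of affected patients can be given.* The documents report no counts for these reactions.
- *The efficacy result is affected.* The ORR definition and the boundaries of 3 responses in 30 and 8 in 50 do not depend on this row.

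**What to change.** Add to the non-hematologic Grade ≥3 row of Table 5:

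*Exception: for the phenytoin and sirolimus reactions listed here (see 6.8.3), the implicated component is permanently stopped and not resumed even if the toxicity recovers. SM-88 and the remaining MPS components may be resumed only if the recovery and 28-day conditions of Table 5, 5.6(b) and 6.8.1 are met, and as allowed by 4.3.12.*

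Then list the reactions:

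- Phenytoin: suspected SJS/TEN; DRESS signs without another established cause; hypersensitivity; acute hepatotoxicity; acute toxicity with levels above the therapeutic range.
- Sirolimus: hypersensitivity; fluid accumulation; angioedema.

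Add a cross-reference to this line in 5.6(b) and in 6.8.1. The second sentence of the exception is needed: without it, the line could be read as letting SM-88 continue through an unresolved Grade ≥3 reaction.

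As an optional clarification outside this conflict, state whether the laboratory-value exception covers a symptom-free transaminase rise judged to be phenytoin hepatotoxicity.

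The cost is one exception line and two cross-references in a single amendment, with no added visits, tests or patients. The downside is brief site retraining and possibly a few more single-component stops.
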